#### 7.1.2. Exclusion Criteria

- Any active anterior segment disease excluding blepharitis;
- Use of any of the following medications (including steroids) up to 12 weeks prior to start of the study or during the course of the study:
  - Ocular medication, category S3 and above;
  - Any systemic or topical medications that will affect ocular physiology e.g. anti-acne medications such as Roaccutane and corticosteroid or immunosuppressant medications such as Hydrocortisone, Prednisolone and antihistamine medications such as Claritine.
- Use of any polyunsaturated fatty acid-containing dietary supplements (such as fish oil, evening primrose oil, linseed oil) for less than 12 weeks prior to the start of the study;
- Planned changes to intake of polyunsaturated fatty acid-containing dietary supplements and/or diet (including typical intake of fish) for the duration of the study;
- Use of any at-home eyelid warming treatments for less than 12 weeks prior to the start of the study, or planned changes to routine usage over the course of the study;
- Use of any of the following dry eye treatments up to 6 months prior to the start of the study or during the course of the study:
  - Intense Pulsed Light (IPL) therapy;
  - Blephasteam;
  - LipiFlow Thermal Pulsation treatment;
  - Punctal plugs.
- Any systemic disease that may affect ocular health e.g. Graves disease, and auto-immune diseases such as ankylosing spondylitis, multiple sclerosis and systemic lupus erythematosus;
- History of eye surgery within 6 months prior to enrolment in the study;

- Epilepsy or history of migraines exacerbated by flashing, strobe-like lights;
- Any known allergy to the ingredients in Systane Complete;
- Pregnancy or breastfeeding.

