| Exclusion criteria   | 
 
○ Allergy to benzoic acid preservatives;
 
○ Allergy to honey products;
 
○ Active anterior eye disease/ infection, inflammation/allergy that requires ocular medical treatment;
 
○ Eye injury or surgery in the past 6 months including chemical burns, penetrating injuries, traumatic iritis, orbital fractures, laser surgery, strabismus surgery, cataract or any other intraocular surgeries;
 
○ Soft contact lens, rigid gas permeable, orthokeratology lens wearer within one week prior to the study and during the study.
 
○ Use of any of the following medications (including steroids) up to 12 weeks prior to start of the study or during the course of the study:             
 
- Ocular medication, category S3 and above;
 
- Any systemic or topical medications that will affect ocular physiology e.g. anti-acne medications such as Roaccutane and corticosteroid or immunosuppressant medications such as Hydrocortisone, Prednisolone and antihistamine medications such as Claritine;
 
 
 
○ Any systemic disease that may affect ocular health e.g. Graves disease, and auto-immune diseases such as ankylosing spondylitis, multiple sclerosis and systemic lupus erythematosus;
 
○ Epilepsy or history of migraines exacerbated by flashing, strobe-like lights;
 
○ The Investigator may, at his/her discretion, exclude anyone else who they believe may not be able to fulfil the study requirements, or if it is believed to be in the participant's best interests.
 
 |
| Human Research Ethics Committee Status / Regulatory Status | 
This trial requires Human Research Ethics Committee approval prior to study initiation, any advertising, and participant consent/enrolment.
 
The study products are commercially available in Australia and are approved by the Therapeutic Goods Administration.
  |

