#### 4.2.1. Risks and Benefits

##### Risks of the Clinical Trial

Although unlikely, it is possible that participants may be allergic to any of the ingredients in the study eye drops. Signs of ocular allergy include swelling, redness, itching and watering of the eyes. Subjects with a known allergy to the study eye drops will not be enrolled. Subjects who experience an allergic reaction will be treated by thoroughly rinsing the eye with preservative free unit-dose saline, continuous monitoring until ocular signs and symptoms have returned to normal, and immediate discontinuation from the study. Subjects may also be referred to the Sydney Eye Hospital for treatment, if required.

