#### 4.2.2. Treatment Rationale

This is a prospective, randomized, double-masked, single centre study. All eligible participants were randomized into one of the treatment groups. One group received Optimel Manuka eye drops (Leptospermum spp. honey 160 mg/g, water, sodium chloride, benzoic acid 0.2 per cent) (Optimel 16 percent), (Melcare, Australia) and the other group received a non-lipid based conventional ocular lubricant, Systane Ultra (Polyethylene Glycol 400 0.4%, Propylene Glycol 0.3%, aminomethylpropanol, boric acid, hydroxypropyl guar, POLYQUAD® (polyquaternium-1) 0.001% preservative, potassium chloride, purified water, sodium chloride, sorbitol)(Alcon

Laboratories, USA). Participants were asked to instill one drop into each eye, three times a day for twenty-eight days ( $\pm 4$  days).

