### 6.1.2. Randomisation and Masking

Prior to initiation of study treatment, each subject who provides informed consent will be assigned to a subject number that will serve as the subject identification number on all study documents. Subject numbers will be assigned in ascending order and should not be omitted or reused.

Participants will be randomly assigned to the eye drop type to be dispensed (Optimel Manuka+16% eye drops or Systane Ultra eye drops). A randomization scheme will be prepared in advance.

The Investigator will provide instructions to the study participants as to the drop instillation technique but will not be cognizant to the randomisation schedule and will not be present during the drop dispensation to maintain masking.

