## SELECTION AND WITHDRAWAL OF PARTICIPANTS

### 7.1. Participant Selection

Participants with dry eye disease will be enrolled. Informed consent will be obtained prior to any clinical trial procedures being conducted. All participants will conform to the clinical trial entry criteria listed below:

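### The only allergy exclusion in section 7.1.2 names Systane Complete, which the trial does not dispense; it omits the synopsis's honey and benzoic acid exclusions, and neither list names Systane Ultra

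*Combined protocol and SAP*

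**What the plan says.** Section 7.1 introduces the entry criteria with "All participants will conform to the clinical trial entry criteria listed below". The exclusion list that follows, in section 7.1.2, has a single item on product allergy: "Any known allergy to the ingredients in Systane Complete".

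The synopsis (Table 1) has a separate exclusion list with two ingredient allergies, "Allergy to benzoic acid preservatives" and "Allergy to honey products". It does not mention Systane Complete.

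Section 6.1.2 states what is dispensed: "Participants will be randomly assigned to the eye drop type to be dispensed (Optimel Manuka+16% eye drops or Systane Ultra eye drops". The synopsis product rows and section 4.2.2 name the same two products.

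Section 4.2.1, under the risks of the trial, makes a general commitment: "Subjects with a known allergy to the study eye drops will not be enrolled".

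Table 4 requires a check of the inclusion and exclusion criteria at Visit 1 but does not say which list is to be used.

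**The concern.** A product-allergy exclusion should keep people with a known allergy to a study drop from being given that drop. As written, the section 7 list asks about a product that is not in the trial and about neither product that is. The synopsis list asks about two ingredients of the test drop and nothing in the control drop. Section 4.2.1 promises more than either list delivers.

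Participant safety is what is mainly at stake. Someone whom section 4.2.1 says must not be enrolled could pass an eligibility check that follows one of the lists faithfully.

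There is also a smaller consequence for the data. Section 4.2.1 discontinues anyone who has an allergic reaction, and section 13.1.3 analyses only those who complete treatment. An avoidable reaction would therefore remove a randomised participant from the analysis for a reason tied to the drop received.

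**Working it through.** The plan gives no figure to reproduce, so the check compares the passages and then counts.

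**1. Is the text current and intact?** The amendment table shows only the final version of 21 March 2018, with the amendment rows blank. The Systane Complete item is a complete sentence with no redaction. It is live wording.

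**2. Which products are in the trial?** The control is Systane Ultra in the synopsis and in sections 4.1, 4.2.2, 5.1, 5.2, 6.1.2, 6.2, 11.1 and 13.1.3. Systane Complete occurs once, in section 7.1.2. (Title, signature and contact pages were not available, so this holds for the text that was.)

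**3. What does each place cover?**

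| Place | Status | Optimel | Systane Ultra |
|---|---|---|---|
| Section 7.1.2 | Entry criterion | Not named; honey and benzoic acid absent | Not named; a different Systane product is |
| Synopsis, Table 1 | Exclusion list in summary | Honey and benzoic acid | Not named, nor any ingredient |
| Section 4.2.1 | Statement in the risk section | Covered in general terms | Covered in general terms |

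Two other synopsis items do not fill the gap. One concerns active eye disease, including allergy that needs ocular treatment, which is not the same as sensitivity to an ingredient. The other lets the investigator exclude at discretion, which gives no specific prompt and is missing from section 7.1.2.

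**4. Ingredient count from section 4.2.2.**

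- Optimel: "Optimel Manuka eye drops (Leptospermum spp. honey 160 mg/g, water, sodium chloride, benzoic acid 0.2 per cent", which is 4 ingredients.
- Systane Ultra: "Polyethylene Glycol 400 0.4%, Propylene Glycol 0.3%, aminomethylpropanol, boric acid, hydroxypropyl guar", which is 5, plus sorbitol, sodium chloride, potassium chloride, purified water and the polyquaternium-1 preservative, another 5. Total 5 + 5 = 10.
- Named in the allergy item of section 7.1.2: 0 of 4 and 0 of 10.
- Named in the synopsis allergy items: 2 of 4 and 0 of 10.

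Water and simple salts are unlikely to call for an allergy item. Leaving them out gives 4 − 2 = 2 for Optimel (water and sodium chloride removed) and 10 − 3 = 7 for Systane Ultra (purified water, sodium chloride and potassium chloride removed). Section 7.1.2 then names 0 of 2 and 0 of 7; the synopsis names 2 of 2 and 0 of 7. The pattern is the same.

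These are counts of what is named. They are not a measure of risk. The documents do not give the composition of Systane Complete, so how far its ingredients overlap with those of Systane Ultra cannot be judged.

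**5. What would a screener be prompted to ask?**

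- Section 7.1.2 alone: nothing about honey or benzoic acid, and a question about a product not in use.
- Synopsis alone: honey and benzoic acid, nothing about Systane Ultra.
- Both lists: honey, benzoic acid and Systane Complete, still nothing that names Systane Ultra.
- Both lists and section 4.2.1: both study drops, in general terms.

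Only the last route meets the commitment in section 4.2.1, and it relies on a sentence outside both lists.

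**The case against.** The strongest reply is that the exclusion is already in the protocol. Section 4.2.1 is categorical, sits in the body of the document and covers both products in full. On allergy the three places add to one another: applied together, they bar everyone this point is about. Harm requires a screener who works from one list and ignores the rest, and nothing describes that practice. The screening form was not available, nor were the consent pages. Visit 1 includes a medical history, and the synopsis allows discretionary exclusion. On this view what remains is a wrong product name and a sentence not repeated.

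Much of this stands. The intent is documented, a miss is not inevitable, and the ingredient fractions describe wording only.

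It does not dispose of the point. Eligibility is checked against criteria, and section 7.1 ties entry to the lists that follow it, not to the risk section. The natural reading is that section 7 governs, although it does not say that it overrides the synopsis. If it does govern, the governing list is the one with the wrong product and nothing for Optimel. If it does not, the document leaves precedence open. A typing error is also too small an explanation: changing the one product name would still leave section 7.1.2 without any allergy item for the test drop. The history may bring an allergy to light, but nothing in it is stated to prompt for these ingredients.

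**Conclusion.** The concern holds as stated. The only allergy exclusion in section 7.1.2 refers to a product the trial does not dispense, the honey and benzoic acid items in the synopsis are absent from it, and neither list names Systane Ultra. The entry criteria therefore do not carry out the commitment in section 4.2.1.

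The consequence is limited to volunteers with a known allergy to a study drop. The documents give no rate for such allergies, so no expected number can be computed and none is claimed. The conclusion assumes only that eligibility is checked against a written criteria list, as Table 4 implies. It does not bear on the sample size, power or error rate. It should be fixed because it is operative eligibility text bearing on safety and is cheap to correct.

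**What to change.** Reconcile the synopsis exclusion list, section 4.2.1 and section 7.1.2, so that the synopsis, section 7.1.2 and the Visit 1 screening check carry one consistent allergy exclusion that matches the commitment in section 4.2.1 and the products dispensed. Resolve the reference to Systane Complete. State which list governs the eligibility check in Table 4. The exact clinical wording is for the investigators to settle.

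The same amendment should reconcile the other differences between the two lists. For example, pregnancy or breastfeeding appears only in section 7.1.2, and eye injury only in the synopsis.

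The cost is a short amendment to the synopsis and section 7.1.2, submitted to the ethics committee as section 15.1.3 requires, and a matching screening form. Power, alpha and the analysis are unaffected.

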## **7.2. Participant Withdrawal**

Participants may be permanently discontinued from the clinical trial for any of the following reasons:

- If, in the Investigator's opinion, it is in the best interest of the participant;
- Persistent clinical trial-related symptoms/complaints that are not correctable;
- Has a serious adverse event/serious adverse event that is eye related and/or which, in the Investigator's opinion, requires withdrawal of the participant;
- Participant voluntarily withdraws consent from the clinical trial (i.e. Revocation of Consent);
- If a participant is not compliant with the clinical trial requirements and instructions;
- Protocol violations/deviations.

## **7.3. Withdrawal and Follow-up Procedure**

This study comprises four visits for each participant. Any participants who wish to be withdrawn from the study will be exited upon request.

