## 6. TRIAL DESIGN

This will be a prospective, randomized, single centre, double-masked, randomized dispensing study. There will be 2 visits in total:

- (i) **Baseline (Week 0):** Screening, randomization, informed consent, habitual visual acuity, OSDI, symptom survey, biomicroscopy, tear film assessment and dispensing eye drops.
- (ii) **28 days of treatment  $\pm$  4 days (Week 4):** habitual visual acuity, OSDI, symptom survey, biomicroscopy, tear film assessment and study exit.

Standard ocular examination and non-standard ocular examination procedures will be carried out at the scheduled visits.

*Standard optometric procedures at each visit include:*

- Habitual visual acuity
- Slit lamp evaluation including corneal details
- Subjective questionnaire: Ocular Surface Disease Index (OSDI)
- Tear breakup time
- Tear lipid layer thickness

*Non-standard optometric procedures may include:*

- Tear evaporation rate

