### 12.4.2. Foreseeable Adverse Events

Risks associated with the use of the study eye drops include:

- Eye discomfort/stinging (<30%)
- Eye redness (<10%)
- Blurry vision (<10%)

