### 12.5. Follow-up

Participants who experience an adverse response will be discontinued from the study and followed up until the condition resolves or the participant is referred to another practitioner.

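### No efficacy measurement is planned for participants who stop before day 28, so the completer result cannot be checked against everyone randomised

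*Combined protocol and SAP*

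**What the plan says.** Section 6 schedules two visits. The second, at day 28 ± 4, is the only one after baseline, and its content is "habitual visual acuity, OSDI, symptom survey, biomicroscopy, tear film assessment and study exit". Table 4 has the same two columns and none for early exit. Section 6.1.4 also counts two visits.

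For people who ask to leave, Section 7.3 states: "Any participants who wish to be withdrawn from the study will be exited upon request". It names no measurements. The same section gives the visit count as four, but no section describes a third or fourth visit.

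Other sections remove participants on the investigator's side:

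- Section 7.2 lists grounds for permanent discontinuation, including "Persistent clinical trial-related symptoms/complaints that are not correctable" and "If a participant is not compliant with the clinical trial requirements and instructions". It equates voluntary withdrawal with revoked consent.
- Section 12.5: "Participants who experience an adverse response will be discontinued from the study and followed up until the condition resolves", or until referral to another practitioner.
- Section 4.2.1, for an allergic reaction: "continuous monitoring until ocular signs and symptoms have returned to normal, and immediate discontinuation from the study".

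Sections 12.2 and 12.4 deal with recording and following adverse events. Section 13.1.3 limits the analysis dataset to people who complete treatment, measures the effect as the change from baseline to day 28, and reports how many discontinued and why. Section 13.3 leaves missing data points out of the analysis of the variable concerned.

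**The concern.** Nothing in the available text separates stopping the drops from leaving the study. A participant whom the investigator discontinues for stinging or an allergic reaction is followed until the eye recovers. That participant is not asked for lipid layer thickness, breakup time, evaporation rate or OSDI at day 28. With no visit between baseline and day 28, no post-baseline efficacy value exists for that person.

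This matters because the loss may be related to treatment. The two drops differ in active ingredients and preservative (Section 4.2.2), and discontinuation can follow symptoms that they cause. If people who tolerate a drop badly leave, those who remain are a selected group, and the selection may differ between arms. The completer comparison could then differ from the comparison of everyone randomised, and the trial would hold no observed data with which to look. Reporting the reasons for discontinuation helps a reader judge the loss but does not supply the missing outcomes.

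**Working it through.** **1. Who has a day 28 value under the plan as written**

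| Route out before Visit 2 | Section | Follow-up requested | Efficacy at day 28 requested |
|---|---|---|---|
| Asks to leave | 7.3 | none named | no |
| Allergic reaction | 4.2.1 | until signs and symptoms are normal | no |
| Adverse response | 12.5, 12.2 | until resolved or referred | no |
| Uncorrectable symptoms, non-compliance, deviation | 7.2 | none named | no |

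Some non-compliant participants may still attend at day 28. Those who revoke consent cannot be measured under any plan.

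**2. The planned allowance**

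Inputs: 38 completers (4.2.4, 13.1.1), 20% dropout and about 48 enrolled (4.2.4), 46 completers (6.1.3).

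- Plan's own figure: 38 / (1 − 0.20) = 47.5, rounded up to 48. It reproduces.
- Planned loss: 48 − 38 = 10, and 10/48 = 20.8%.
- Under 6.1.3: 48 − 46 = 2, and 2/48 = 4.2%. Since 38 × 1.2 = 45.6, the 46 may be a mislabelled enrolment figure; this is an inference.

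Two limits apply to the figure of 10. If each of 48 left independently with probability 0.20 (an assumption), the binomial probability of more than 10 leaving is 0.36. In the other direction, Section 6.1.5 counts a person as enrolled at consent, so some of the 10 may go before randomisation.

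**3. Illustrative shift in the completer contrast**

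Assumptions, none of them in the documents: 24 randomised per arm, all 10 leavers randomised, and a gap d, in SD units, between the mean of stayers and the mean that leavers would have had. In one arm, the completer mean minus the all-randomised mean is p × d, where p = leavers/24. The contrast shifts by p₁d₁ − p₂d₂. With 38 completers split evenly, its standard error is √(4/38) = 0.324 SD.

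| Leavers by arm | Gap | Shift |
|---|---|---|
| 5:5 | same d in both arms | 0 |
| 6:4 | same d in both arms | (6 − 4)/24 = 0.083d |
| 7:3 | same d in both arms | (7 − 3)/24 = 0.167d |
| 5:5 | 1 SD in one arm, 0 in the other | 5/24 = 0.21 SD |

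At d = 1 the 7:3 row is 0.167/0.324 = 0.51 standard errors. The last row is 0.208/0.324 = 0.64 standard errors, although dropout is perfectly balanced. With 2 leavers split 2:0, the shift is 2/24 = 0.083d. These rows show how the shift behaves. They are neither estimates nor bounds.

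**The case against.** The strongest case against is that no bias is shown. The documents give no dropout by arm or reason, no gap between stayers and leavers, and no SD. Section 12.4.2 lists discomfort or stinging at under 30% for the study drops together. That is a symptom frequency, neither a discontinuation rate nor a difference between arms. This stands: treatment-related loss is possible, not demonstrated.

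A second objection is that values taken off drops do not answer the question in Section 6.2, which concerns lipid layer thickness after four weeks of daily use. People who stop may be using other eye products or be under treatment. This also stands, and it is why the added analysis should sit beside the completer analysis and not replace it.

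Third, the root is the completer-only dataset in Section 13.1.3, and extra measurements matter only if an analysis uses them. That is true, so the two changes belong together. But the analysis cannot be widened later if the measurements were never taken.

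A reader might infer more than the documents support in three ways:

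- **That at most 10 people can be affected.** Nothing caps the loss at the planning allowance.
- **That the bias is at most about half a standard error.** This holds only for the splits considered, gaps of no more than 1 SD and an equal gap in both arms. Unequal gaps exceed it even at 5:5.
- **That inviting people back would cut the bias by a known amount.** This requires returners to be a random sample of leavers, with the same outcome on and off drops. The documents support neither.

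**Conclusion.** The gap is real and follows directly from the text: one post-baseline efficacy visit, several routes out before it, and no request for efficacy data on any of them. Because some of those routes are tied to drop-related symptoms and only completers are analysed, the completer result cannot be checked against everyone randomised.

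The planned loss is about 10 of 48 enrolled, or 2 of 48 under Section 6.1.3. The number who are randomised, leave early and could still be measured is an unknown part of the actual loss. The size and direction of any bias are unknown. This is an inexpensive improvement to consider, not evidence that the planned comparison is biased. The four-visit count in Section 7.3 is an editorial slip and does not cause the gap.

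**What to change.** 1. In Sections 7.3 and 12.5 and in a note to Table 4, separate stopping the drops from revoking consent. Invite every randomised participant who stops or is discontinued, and has not revoked consent, to the existing day 28 ± 4 Visit 2 measurements. Record the date of the last drop and any other eye treatment used since.
2. In Section 13.1.3, keep the completer analysis and add a sensitivity analysis of all randomised participants with day 28 data, grouped by assigned drop. Label it as answering an all-randomised question, not the on-treatment one in Section 6.2.
3. Editorial: change the visit count in Section 7.3 from four to two.

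The cost is a few sentences, plus about ten or fewer extra one-hour visits if dropout is as planned and more if it is higher, using existing procedures and equipment. The budget effect cannot be checked, because Section 16 refers financing to a separate agreement. Some participants will decline, those who revoke consent are not reached, and some values will be off-drop. The completer contrast itself does not change.
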